Statistical Methods:	
Efficacy Data from all subjects who complete at least the first 4 weeks of the study drug (placebo or active) will be included in the efficacy analysis. Subjects whose biomarkers (CSF or amyloid PET) are found to be unsupportive of AD after they enroll in the trial will be excluded from the efficacy analysis. Subjects who decline to have CSF or amyloid-PET imaging will not be excluded from the efficacy analysis.
 
Cognitive, behavioral and functional measures, as well as M/EEG epileptiform activity, power spectral density for different frequency bands, and MEG-I functional connectivity at study days 1, 29, 57, and 85 will be recorded and summarized. Descriptive statistics will be generated as appropriate (i.e., mean, median, range, and standard deviation for continuous data and frequency for categorical data).
 
Each treatment effect will be tested for the assumption of normality. If the data are not normally distributed, we will investigate transforming data so they are normally distributed or nonparametric options. If we choose parametric tests, significance testing will be performed using analysis of variance (ANOVA) for repeated measures with drug treatment (LEV or placebo) as the independent variable. Prior to this analysis, ANOVA will be used to analyze the effect of drug-placebo sequence and to compare group demographics and severity of dementia at baseline (MMSE and CDR-SOB); if any of these factors confound the relationship between the study drug and the outcome measure, then they will be included as covariates in the ANOVA model. If factors arise that limit the appropriateness of the repeated-measures ANOVA model, such as a large dropout rate or varying data collection time points causing imbalance of longitudinal data, we will substitute a linear mixed effects regression model to better fit the longitudinal data without the intrinsic constraints of the repeated-measures ANOVA framework (Fitzmaurice et al. 2004, Finucane et al. 2007). If a drug carryover effect is observed on an outcome measure between weeks 4 and 8, then we will analyze the initial 4 weeks of the study separately for this outcome measure. Analyses will be two-tailed except for analysis of epileptiform activity, which will be one-tailed based on our expectation that LEV will reduce epileptiform activity (Sanchez et al. 2012, Mintz et al. 2009). For all analyses, the null hypotheses will be rejected at $p < 0.05$.
 
For the exploratory whole-brain MEG-I functional connectivity analyses, corrections for multiple comparisons will be performed using a cluster correction with a cutoff level of 20 voxels, and p values thresholded to 0.01. If no significant voxels are found at this threshold, we will use a less stringent threshold of $p < 0.05$. A hierarchical validation analysis will be used to account for multiple cognitive, behavioral, and functional tests.

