10.2 Statistical Analysis of Efficacy Data

Data from all subjects who complete at least the first 4 weeks of the study drug (placebo or active) will be included in the efficacy analysis. Subjects whose biomarkers (CSF or amyloid PET) are found to be unsupportive of AD after they enroll in the trial will be excluded from the efficacy analysis.

Cognitive, behavioral and functional measures, as well as M/EEG epileptiform activity, power spectral density for different frequency bands, neural activity during cognitive tasks, and MEG-I functional connectivity at study days 1, 29, 57, and 85 will be recorded and summarized. Descriptive statistics will be generated as appropriate (i.e., mean, median, range, and standard deviation for continuous data and frequency for categorical data).

Each treatment effect will be tested for the assumption of normality. If the data are not normally distributed, we will investigate transforming data so they are normally distributed or nonparametric options. If we choose parametric tests, significance testing will be performed using ANOVA for repeated measures with drug treatment (LEV or placebo) as the independent variable. Prior to this analysis, ANOVA will be used to analyze the effect of drug-placebo sequence and to compare group demographics and severity of dementia at baseline (MMSE and CDR-SOB); if any of these factors confound the relationship between the study drug and the outcome measure, then they will be included as covariates in the ANOVA model. If factors arise that limit the appropriateness of the repeated-measures ANOVA model, such as a large dropout rate or varying data collection time points causing imbalance of longitudinal data, we will substitute a linear mixed effects regression model to better fit the longitudinal data without the intrinsic constraints of the repeated-measures ANOVA framework (Fitzmaurice et al. 2004, Finucane et al. 2007). If a drug carryover effect is observed on an outcome measure between weeks 4 and 8, then we will analyze the initial 4 weeks of the study separately for this outcome measure. Analyses will be two-tailed except for analysis of epileptiform activity, which will be one-tailed based on our expectation that LEV will reduce

epileptiform activity (Sanchez et al. 2012, Mintz et al. 2009). For all analyses, the null hypotheses will be rejected at $p < 0.05$.

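### The crossover analysis names no period term, so any shift in scores between the two treatment periods goes into the error and costs precision and power

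*Combined protocol and SAP*

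**What the plan says.** Section 10.2 gives the parametric analysis in one clause: "significance testing will be performed using ANOVA for repeated measures with drug treatment (LEV or placebo) as the independent variable". The synopsis (Statistical Methods) gives the same single factor, "with drug treatment (LEV or placebo) as the independent variable", and section 10.2 uses it again for the Virtual Route learning-rate and asymptote parameters.

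Other factors are conditional. The text says "Prior to this analysis, ANOVA will be used to analyze the effect of drug-placebo sequence" and to compare demographics, MMSE and CDR-SOB between groups; then "if any of these factors confound the relationship between the study drug and the outcome measure, then they will be included as covariates". If dropout or irregular visit times make the ANOVA unsuitable, "we will substitute a linear mixed effects regression model to better fit the longitudinal data", with no fixed or random effects named.

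The analysis set includes people with one period only: "Data from all subjects who complete at least the first 4 weeks of the study drug (placebo or active) will be included". For non-normal data, "we will investigate transforming data so they are normally distributed or nonparametric options". On sidedness: "Analyses will be two-tailed except for analysis of epileptiform activity, which will be one-tailed".

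Neither the synopsis nor section 10 names period, visit or time as a model term. Period is unspecified rather than explicitly excluded.

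**The concern.** In a two-period crossover each subject's LEV-minus-placebo difference contains the drug effect plus or minus whatever changed between the periods. Subjects take the battery four times in 12 weeks, so practice, disease progression or unequal test forms could all move scores. A period term removes that movement; a drug-only model leaves it in the residual.

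The factors that may be added conditionally are constant within a subject. Entered as main effects, they leave the treatment contrast in complete pairs unchanged and cannot absorb a period shift. The carryover rule addresses persisting drug effect, which is a different problem.

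At stake are power and interval width on the primary endpoint and, if the analysed sequences are unequal, some bias of either sign. The planned power has little slack for avoidable error variance.

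**Working it through.** **Inputs from the documents.** 36 subjects (section 3); 10% dropout, effect size 0.356 and power above 0.8 (section 10.1); two-sided 5% for the primary endpoint (section 10.2); randomisation four at a time to two sequences (section 5.2). 36 × 0.9 = 32.4, taken as 32 completers.

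**Assumptions, not in the documents.** π is the period-2 minus period-1 shift, in SDs of the paired difference; ρ is the within-subject correlation; 0.356 is read as Cohen's f, so d = 2 × 0.356 = 0.712.

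**Step 1: the plan's own figure.** For two within-subject levels the noncentrality is λ = 2nf²/(1 − ρ). With ρ = 0 this is a paired t-test with standardised effect 0.356 × √2 = 0.503. Power is 0.788 at n = 32, 0.801 at n = 33 and 0.836 at n = 36. The stated power reproduces, at the margin.

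**Step 2: what omission does.** Let A be LEV first and B placebo first, and let δ be the standardised drug effect, δ = 0.712/√(2(1 − ρ)) = 0.503, 0.712 and 0.919 at ρ = 0, 0.5 and 0.7. The paired difference has mean δ − π in A and δ + π in B, with SD 1.

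- Bias of the drug-only estimate: π(nB − nA)/n. This is zero at 16:16, π/16 in size at 17:15 and π/8 at 18:14.
- Standard error inflation at 16:16: √(1 + π² × 32/31) = 1.032, 1.122 and 1.426 at π = 0.25, 0.5 and 1.0.
- Completers needed to regain the lost precision, 32(1 + π²): 34, 40 and 64.

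**Step 3: power at 16:16** (simulation, drug-only one-sample t against the period-adjusted crossover t).

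| | π = 0.25 | π = 0.5 | π = 1.0 | With period term |
|---|---|---|---|---|
| Power, ρ = 0 | 0.77 | 0.71 | 0.48 | 0.79 |
| Power, ρ = 0.5 | 0.97 | 0.954 | 0.86 | 0.97 |
| Power, ρ = 0.7 | 0.999 | 0.998 | 0.986 | 0.999 |
| Type I error | 4.4% | 2.9% | 0.6% | 5% |
| Interval wider by | 3% | 12% | 43% | – |
| Effect detectable at 80% power (SD of difference) | 0.52 | 0.56 | 0.67 | 0.51 |

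In outcome SDs the three shifts are 0.35, 0.71 and 1.41 at ρ = 0; 0.25, 0.5 and 1.0 at ρ = 0.5; and 0.19, 0.39 and 0.77 at ρ = 0.7. If every withdrawal is replaced (18:18), power at ρ = 0 is 0.82, 0.77 and 0.56 against 0.84.

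**Step 4: unequal sequences.** At 18:14, with all four expected losses in one sequence, two-sided type I error still stays below 5%, but bias moves power either way. For a 0.5 SD improvement in period 2 at ρ = 0, power without the term is 0.59 if the LEV-first group is larger and 0.82 if it is smaller, against 0.78 with the term.

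**Step 5: the one-tailed epileptiform subset** (about 12 subjects). Averaged over possible splits, type I error of the t-test is 4.8%, 4.5% and 3.6% at the three shifts, so there is no overall inflation. Given a split that favours LEV and π of 0.5 to 1.0, it is 10–12% at 8/4 and 16–28% at 9/3. Splits at least that uneven in that direction have probability 14% and 3.8%. The documents give no evidence that spike counts shift.

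**The case against.** The strongest reply is that the plan may already cover period. If sequence is crossed with drug, the drug-by-sequence interaction in a two-by-two crossover is the period effect, and the drug test equals the period-adjusted test. In complete pairs a sequence main effect cannot alter the drug comparison, so this reading arguably gives the confounding rule its only content. Read as a 5% pre-test, it gives power of 0.784, 0.785 and 0.787 at ρ = 0, so almost nothing is lost. This stands as a possible reading. However, the text speaks of covariates, states no interaction and keeps inclusion conditional.

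Second, all measures are repeated on day 57, and section 9 describes efficacy endpoints as changes. If change from each period's own baseline is analysed, linear progression and any shift already present on day 57 cancel, leaving only unequal change across periods. That could shrink π considerably. The plan does not say which quantity is modelled, and practice gained mostly between the first two tests would still leave a shift.

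Third, the large losses need extreme inputs. A shift of 1.0 SD of the paired difference, or zero within-subject correlation, has no support in the documents, and sections 9.1 and 9.3 provide four alternative forms of the NIH EXAMINER and ADAS-cog. For shifts of 0.1 to 0.3 outcome SD at ρ = 0.5, power without the term is 0.973 to 0.968, against 0.973 to 0.974 with it, and the interval is 0.5% to 4% wider. This limits the expected size. It does not supply a reason to omit the term.

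**Conclusion.** The concern holds. Drug is the only unconditional factor in the ANOVA, the fallback model has no stated terms, and period is specified in neither. That part is certain.

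The consequence with near-balanced sequences is lost precision and a conservative test, not false positives. Its size runs from negligible (small shift or high correlation) to large: about 8 points of power at π = 0.5 and 30 points at π = 1.0 when ρ = 0. Those figures depend on π and ρ, which the documents do not give, and on reading 0.356 as Cohen's f. If the sequence check was meant as a test for period, the loss almost disappears and the defect is mainly one of wording. The point should be fixed because the remedy is nearly free; it does not invalidate the trial.

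**What to change.** Prespecify as the primary analysis a linear mixed model with fixed effects for treatment, period and sequence and a random subject effect, all unconditional. Use the same period adjustment for the Virtual Route parameters, and a period-adjusted transformed or rank-based test for spike counts. State whether the outcome is the end-of-period score or change from that period's baseline. If the sequence check was intended to detect a period effect, say so and replace it with the fixed term.

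The cost is SAP wording and one degree of freedom. With no shift and ρ = 0, power with and without the term is 0.787 and 0.788 at 16:16, and 0.780 and 0.788 at 18:14. The model also gives a defined analysis for subjects with only the first 4 weeks. Adding four such subjects to 32 completers lowers the standard error by 2.8%, 1.4% and 0.8% at ρ = 0, 0.5 and 0.7, a small gain.

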7. To explore the effects of LEV versus placebo on all primary, secondary, and exploratory measures listed above in the following subgroups:

- a. AD subjects with clinical signs of neuronal hyperexcitability including one or more of the following:
 - a. One or more unprovoked seizures within 5 years of screening,
 - b. Epileptiform activity within 5 years of screening,
 - c. Epileptiform activity on their initial overnight EEG or M/EEG, or
 - d. Epileptiform activity on either of their baseline M/EEGs (study days 1 and 57)
- b. AD subjects without clinical signs of neuronal hyperexcitability listed in (a)
- c. Early-onset AD (symptom onset < 65 years of age)
- d. Late-onset AD (symptom onset \geq 65 years of age)
- e. AD with predominant language impairment (AD-language) (Gorno-Tempini et al. 2011)
- f. AD with predominant posterior cortical atrophy (AD-PCA) (Mendez et al. 2002)
- g. AD patients not classified as AD-language or AD-PCA
- h. Very mild AD (MMSE of 24 and above)
- i. Mild to moderate AD (MMSE of 18 to 23)
- j. Subjects taking memantine
- k. Subjects not taking memantine
- l. Carriers the apolipoprotein E4 allele (obtained through umbrella projects)
- m. Noncarriers the apolipoprotein E4 allele.

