9. ASSESSMENT OF EFFICACY

The efficacy endpoints for this trial include changes in epileptiform activity, cognition, degree of disability, and behavior. The exploratory endpoints for this trial include changes in cognition (novel tasks and subcomponents of established standardized tasks), clinical fluctuations, MEG power spectrum, MEG-I functional connectivity, blood prolactin levels, and subgroup analysis of all efficacy measures.

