10. STATISTICS

10.1 Sample Size Considerations

We based sample-size estimates on our hypotheses that LEV will improve cognitive performance to an extent that is clinically meaningful, compared to placebo. Standard sample-size calculations for repeated measures analysis of variance (ANOVA) (Cohen 1988) show that F tests could detect an effect size of 0.356 with power greater than 0.8 with our sample sizes, allowing for a 10% dropout rate.

For the M/EEG exams, if we observe epileptiform activity in 12 of our subjects (33%), as predicted by our preliminary data, we should be powered to detect small reductions in epileptiform activity during LEV treatment compared to placebo. As a reference, 10 hAPP mice provided robust power to detect a 40% reduction ($p<0.0005$) in spike frequency with chronic LEV administration compared to baseline (Sanchez et al. 2012).

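### An undefined carryover check triggers a first-4-weeks analysis for any outcome, including the primary, and the plan does not say which result then governs

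*Combined protocol and SAP*

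**What the plan says.** The main efficacy analysis in Section 10.2, if parametric, is "ANOVA for repeated measures with drug treatment (LEV or placebo) as the independent variable". One conditional sentence follows, repeated in the synopsis under Statistical Methods: "If a drug carryover effect is observed on an outcome measure between weeks 4 and 8, then we will analyze the initial 4 weeks". Its consequence is that "we will analyze the initial 4 weeks of the study separately for this outcome measure".

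The time window is given. These items are not given in any section:

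- the contrast: Day 57 alone or relative to Day 1 or Day 29, and between sequences or within the LEV-first group;
- the test and threshold that make carryover observed;
- the form of the first-4-weeks analysis;
- whether that result replaces the crossover result or sits beside it, and which of the two decides the primary.

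The nearest related step is a preliminary one: "Prior to this analysis, ANOVA will be used to analyze the effect of drug-placebo sequence". Its stated consequence is adding a covariate, not moving to first-period data.

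**The concern.** A crossover plan that lets a preliminary look at carryover bring in a first-period analysis has two stages, and its error rates depend on both. Here the first stage is undefined and the role of the second is unstated. It applies outcome by outcome with no exception for NIH EXAMINER.

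Whether the first-period result replaces or supplements the crossover does not settle the matter. Under replacement, an undefined check decides which analysis counts. Under supplementation, a flagged outcome has two results and no rule for which one supports the claim. Either way, the choice can be made with the data in view. What is at stake is the credibility of the primary conclusion, some power, and a little type I error.

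**Working it through.** **Inputs from the documents**

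- 36 subjects (Section 3) and 10% dropout (10.1): 36 × 0.9 = 32.4, taken as 32. Randomization in fours (5.2) gives about 16 per sequence.
- Effect size 0.356, metric not named (10.1).
- Two-tailed p < 0.05 (10.2).
- Half-life of 6-8 hours (1.2) and a 4-week washout (Section 3).

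**Assumed, not in the documents**

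- Four normally distributed visits with equal correlation ρ of 0, 0.5 or 0.8.
- A between-sequence check on Day 57 or on Day 57 minus Day 1, at 0.05 unless stated.
- No true carryover unless stated.
- Crossover = comparison between sequences of Day 29 minus Day 85.

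**Step 1. The plan's own figure.** Section 10.1 says that "F tests could detect an effect size of 0.356 with power greater than 0.8 with our sample sizes". Read as Cohen's f for two conditions, the mean difference is 2 × 0.356 = 0.712 SD. At ρ = 0, dz = 0.712/√2 = 0.503. The non-central t with n = 32 (non-centrality 0.503 × √32 = 2.85) gives power 0.788, and n = 33 gives 0.801. The figure is reproduced to within about a point. Reading 0.356 as dz gives only 0.497. The reference power below is 0.79.

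**Step 2. First-period power.** Hold dz at 0.503, so d = 0.503 × √(2(1−ρ)) = 0.712, 0.503 and 0.318 SD at ρ = 0, 0.5 and 0.8. The Day 1-adjusted comparison of 16 with 16 then has simulated power 0.48 down to 0.30, against 0.79 for the crossover.

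**Step 3. How often the open choice matters.** With no carryover the check flags about 5% of trials per outcome. The two analyses disagree on significance in 35-53% of all trials, flagged or not, because one is much weaker. Flag and disagreement together: 0.05 × 0.35 = 1.8% to 0.05 × 0.53 = 2.7% of trials, which simulation confirms. Cases where the first period is significant and the crossover is not make up only 0.1-0.2% of trials. Nearly all the rest are the first-period analysis missing a real effect.

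**Step 4. Power under replacement.** As an approximation, 0.95 × 0.79 + 0.05 × 0.48 = 0.77, and 0.95 × 0.79 + 0.05 × 0.30 = 0.77. Simulated across first-period forms (raw Day 29, change from Day 1, Day 1-adjusted) the result is 0.75-0.77.

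**Step 5. Type I error (raw crossover, checks at 0.05 or 0.10)**

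| Version | Replacement | Either result claimable |
|---|---|---|
| Day 57 minus Day 1 check, Day 1-adjusted first period | 0.050-0.057 | 0.052-0.060 |
| Worst pairing: raw Day 57 check at 0.10, raw Day 29 first period | up to 0.076 | up to 0.079 |

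**Step 6. Does the check find real carryover?** If the whole effect persists and dz is 0.50, Day 57 flags 14-49% of trials (depending on ρ) and Day 57 minus Day 1 flags 28%. If the effect is held at 0.712 SD and ρ = 0.8, Day 57 minus Day 1 flags 87%. Detection therefore depends on effect size and correlation.

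**Step 7. Bias of the crossover under carryover.** Let a fraction c of the effect d persist evenly to Day 85 in LEV-first subjects. The sequence difference in Day 29 minus Day 85 is d(1−c) + d. Halved, it is d(1 − c/2): 75% of the true effect at c = 0.5 and 50% at c = 1. At dz 0.50 the crossover's power is then 0.54 and 0.28. The two-stage rule gives 0.48-0.55 and 0.24-0.39 with these checks.

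**Step 8. Residual drug.** 28 × 24/8 = 84 and 28 × 24/6 = 112 half-lives of washout.

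**The case against.** The strongest defence is that the sentence is harmless and readable. The word separately leans toward an added analysis, the general p < 0.05 sentence could serve as the threshold, and the sequence ANOVA could be the check. None of these closes the gap. If the analysis is added, the plan still does not say which result decides. The p < 0.05 sentence is not tied to carryover being observed. The sequence ANOVA leads only to a covariate.

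A second defence is that a switch has merit. Section 1.2 cites improvement of network and synaptic dysfunction in mice, so a lasting effect is not excluded, and under full persistence the two-stage rule can reach power 0.39 against 0.28. This stands. Making the crossover govern is a choice with a cost; what the gap strictly requires is that the rule be defined in advance.

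Several stronger readings are tempting and are not supported:

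- *That the plan requires replacement.* It does not say so.
- *That a flag itself makes the analyses conflict.* They disagree about as often without a flag (Step 3).
- *That the rule invites many favourable claims or serious type I inflation.* The favourable case is 0.1-0.2% of trials, and the inflation is small except in one pairing.
- *That a Day 57 check cannot detect carryover.* Step 6 shows it sometimes can.
- *That Day 57 minus Day 29 should be counted as the check.* That would label ordinary loss of effect after stopping drug as carryover.

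Which scores enter the crossover model is also unclear: Section 9 says that "The efficacy endpoints for this trial include changes in epileptiform activity, cognition, degree of disability, and behavior", while 10.2 names only the treatment factor. That is a separate gap and is not counted here.

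**Conclusion.** The point holds as a gap in pre-specification. The contrast, threshold and governing result are missing for a rule that reaches the primary outcome, so the governing result can be picked after the data are seen. That conclusion rests on the text alone.

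The size is modest: a loss of about 2 to 4 points of power under replacement, and type I error mostly within a point of nominal, reaching about 0.08 only in the worst pairing. These figures depend on the assumed correlations, on reading 0.356 as Cohen's f, and on 16 completers per sequence. The long washout relative to half-life makes residual drug an unlikely cause of a flag, so chance would be a common one; a lasting effect remains possible. Confidence is high that the rule is open and moderate on the numbers. Label: cheap improvement.

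**What to change.** In Section 10.2 and the synopsis, replace the conditional sentence with three statements:

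1. The period-adjusted, within-subject crossover analysis governs for every outcome, whatever any carryover check shows.
2. The first-period, Day 1-adjusted estimate is reported for all outcomes as a labelled sensitivity analysis.
3. Day 57 versus Day 1 is shown by sequence descriptively.

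If a switch is preferred, name the contrast, the threshold and the governing result in advance. Day 57 minus Day 1 with a Day 1-adjusted first period costs least (power about 0.77 against 0.79).

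The cost is wording plus IRB approval; no new visit or measurement is needed. The plan should state the downside: if the effect persists to Day 85, the raw crossover estimate is biased toward zero by the amounts in Step 7, and a two-stage rule would sometimes have more power. The first-period sensitivity estimate is free of that bias, though its power is only 0.30-0.48.

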Criteria for Evaluation:	
Primary Endpoints The efficacy of LEV to improve executive function (NIH EXAMINER) in patients with AD is the primary endpoint for this trial.
 
Secondary Endpoint The efficacy of LEV to suppress epileptiform activity (M/EEG), to improve cognitive function (Stroop interference naming and ADAS-cog), and to improve the degree of disability (CDR-SOB, ADCS-ADL, and ADCS-CGIC) and behavior (NPI) in patients with AD are the secondary endpoints for this trial.
 
Exploratory Endpoints We have the following exploratory endpoints for patients with AD:
 
 1. Effects of LEV on learning and memory using a computerized Virtual Route Learning Test. 2. Effects of LEV on Stroop color naming correct, Stroop color naming errors (uncorrected and self-corrected), and Stroop interference naming errors (uncorrected and self-corrected), and subcomponents of the ADAS-cog (learning and memory, language, constructional praxis, ideational praxis, and orientation). 3. Effect of LEV on clinical fluctuations using two standardized scales (Walker et al. 2000). 4. Effect of LEV on MEG power spectrum (delta, theta, alpha, beta and gamma activity) measures during rest and neural activity during cognitive stimulation. 5. Effect of LEV on MEG functional connectivity measures in brain regions that correlate with performance on NIH EXAMINER (composite and each component), ADAS-cog (composite and each component), Stroop Test, Virtual Route Learning Test with 4-hour recall, Clinician Assessment of Fluctuation, One Day Fluctuation Assessment, CDR-SOB, ADCS-ADL, ADCS-CGIC, and NPI (composite and each component). 6. Effect of LEV on serum prolactin levels. 7. Effects of LEV on all primary, secondary, and exploratory endpoints listed above in the following subgroups: 
 a. AD subjects with seizures or epileptiform activity, b. AD subjects without seizures or epileptiform activity, c. Early-onset AD (symptom onset < 65 years of age), d. Late-onset AD (symptom onset ≥ 65 years of age), e. AD-language (Gorno-Tempini et al. 2011), f. AD-PCA (Mendez et al. 2002), g. AD patients not classified as AD-language or AD-PCA, h. Very mild AD (MMSE of 24 and above), i. Mild to moderate AD (MMSE of 18 to 23), j. Subjects taking memantine, k. Subjects not taking memantine, l. Carriers the apolipoprotein E4 allele, and m. Noncarriers of the apolipoprotein E4 allele

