For the Virtual Route Learning Task, we will measure total accuracy summed across trials 2 through 15 (max score = 210) and accuracy at the delay trials (max score = 15). We will also explore the trial-by-trial accuracy, error rates, learning rates and asymptotes. The preliminary data suggest a 2 parameter exponential model will provide a good fit for the learning data. We will compare estimated learning rates and asymptotes parameters using ANOVA for repeated measures with drug treatment (LEV or placebo) as the independent variable. However, if additional data collection suggests that simple slopes better summarize the data, then we will use linear mixed effects models. If we use linear mixed effects models and residuals are not normally distributed, we will use bootstrapping techniques to produce reliable standard errors.

For the whole-brain MEG-I functional connectivity analyses, neuropsychological, behavioral, and functional measures from each subject will be correlated with global connectivity values at each voxel using the Pearson's correlation. Corrections for multiple comparisons will be performed using a cluster correction with a cutoff level of 20 voxels, and p values thresholded to 0.01. If no significant voxels are found at this threshold, we will use a less stringent threshold of $p < 0.05$. A hierarchical validation analysis will be used to account for multiple cognitive, behavioral, and functional tests.

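### Section 10.2 rejects every null at p < 0.05, including seven secondary endpoints and all measures in 13 subgroups, and the only multiplicity procedure named for clinical tests is undefined

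*Combined protocol and SAP*

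**What the plan says.** The decision rule is in Section 10.2 and again under Statistical Methods in the synopsis: "For all analyses, the null hypotheses will be rejected at" p < 0.05. No tier of endpoint is exempt. On sidedness, Section 10.2 adds: "Analyses will be two-tailed except for analysis of epileptiform activity, which will be one-tailed".

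The tests under that rule are:

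- **Primary.** One endpoint. The synopsis states: "The efficacy of LEV to improve executive function (NIH EXAMINER) in patients with AD is the primary endpoint for this trial".
- **Secondary.** Seven endpoints (synopsis, Criteria for Evaluation; Section 2.2): M/EEG epileptiform activity, Stroop interference naming, ADAS-cog, CDR-SOB, ADCS-ADL, ADCS-CGIC and NPI.
- **Subgroups.** Section 2.3, item 7: "To explore the effects of LEV versus placebo on all primary, secondary, and exploratory measures listed above in the following subgroups". The list runs from a to m, which is 13 subgroups.

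Multiplicity is mentioned only in the MEG-I paragraph that closes Section 10.2 and in its synopsis counterpart. That paragraph gives a voxel cluster correction at p 0.01, relaxed to p < 0.05 if nothing is found. It then ends with: "A hierarchical validation analysis will be used to account for multiple cognitive, behavioral, and functional tests". Nothing further is said about that analysis.

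**The concern.** The secondary objectives on epileptiform activity and cognition are worded as determining efficacy, and the plan gives a rule for declaring each of them significant. The subgroup objective is exploratory, but the same rule applies there. Version 3 added four subgroups to examine whether patients with hyperexcitability or early-onset disease respond better, so those results will be read and interpreted.

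In a 36-subject trial this combination can produce rejected nulls from chance alone. A reader who sees that multiple tests are accounted for may assume the error rate is controlled. As written, nobody could carry out the named procedure or check that it had been followed.

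**Working it through.** **1. The plan's own figure.** The documents state no family-wise error rate. The nearest figure is in Section 10.1: effect size 0.356, power above 0.8, 10% dropout. From 36 subjects, 36 × 0.9 = 32.4, so about 32 remain. I read 0.356 as Cohen's f, which is an assumption, and treat the two conditions as independent sets of 32. Then λ = 64 × 0.356² = 8.11, and F(1, 62) at α = 0.05 gives power 0.801. Other readings give other powers; a paired test with a standardized difference of 0.356, for example, gives 0.497. The reading that reproduces the claim uses a single test at 0.05, with no allowance for multiple tests.

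**2. Primary endpoint.** One endpoint, one test, error 5.0%. Later tests do not change it.

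**3. Seven secondaries, no effect on any.** Each test has a 0.05 chance of a false rejection. This includes M/EEG, where the whole 0.05 lies in one tail.

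- Independent: 1 − 0.95⁷ = 0.302. With the primary added: 1 − 0.95⁸ = 0.337.
- Counting only false rejections in the direction of benefit, independent: 1 − 0.95 × 0.975⁶ = 0.184.
- Correlated, by simulation with one common correlation and M/EEG one-sided:

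| Assumed correlation | At least one false rejection in 7 |
|---|---|
| 0 | 30.2% |
| 0.3 | 27.3% |
| 0.5 | 23.3% |
| 0.7 | 18.4% |

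The correlations are assumptions; the documents give none.

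**4. Subgroups.** Eight measures (one primary, seven secondary) × 13 subgroups = 104 tests. Two of these need adjusting:

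- The epileptiform endpoint is assessed only in those with epileptiform activity on a baseline M/EEG (Section 2.2, item 1).
- By the definition in Section 2.3, item 7, all such subjects fall in subgroup a and none in b. The test in b cannot exist, which leaves 103.
- The test in a repeats the main secondary test, which leaves 102 distinct new tests.

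Expected false rejections under no effect are 102 × 0.05 = 5.1 to 104 × 0.05 = 5.2. Expectations add whatever the dependence, so correlation between measures or overlap between subgroups does not change this count.

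Correlation does change the chance of at least one. It is 1 − 0.95¹⁰⁴ = 99.5% if independent, and about 97% down to 86% in simulation at correlations of 0 to 0.7. The simulation used 32 subjects, all 104 tests two-sided, and overlapping subgroups. The splits were assumed: 33/67 for hyperexcitability, 20/20/60 for phenotype, 50/50 otherwise. Exploratory measures in the same subgroups would add further tests.

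**5. Can the hierarchical sentence be applied?** A working procedure needs the endpoints covered, their order or families, the level at each step, and a rule for stopping. Section 10.2 and the synopsis give none of these. Two readings of its scope are possible:

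- *MEG-I only.* The sentence sits in the MEG-I paragraph, and in the synopsis that paragraph is introduced as exploratory. The secondaries and subgroups would then have no adjustment.
- *All clinical tests.* Its words match the categories of measure used earlier in Section 10.2. The secondaries would then be covered, but by a procedure that cannot be executed as written.

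Neither reading yields verifiable control.

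**The case against.** The strongest reply is that this is a small phase 2a trial with one named primary endpoint and clearly ranked tiers. Every subgroup analysis is labelled exploratory, and many such trials report secondary results unadjusted. That largely stands. It means the remedy should be modest, not that the rule can stay: the labels do not alter a sentence that rejects nulls in all analyses.

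Four stronger readings may tempt a reader, and the documents do not support them.

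- *That the primary result is compromised.* It is a single endpoint tested once, and its 5% is intact.
- *That nothing outside MEG-I is adjusted, or that the hierarchical sentence contradicts p < 0.05.* The scope of the sentence is ambiguous, so the first is unproven. The second does not follow: a fixed-sequence procedure tests each step at the full 0.05 and still controls the family-wise error. The defect is that the procedure is undefined.
- *That a significant secondary result is likely to be chance, or that false effects are sure to be declared.* For the secondaries the figure is about 18% to 30%. Only the subgroup family approaches certainty.
- *That secondary and subgroup findings would have the same standing as the primary.* The ranking of objectives is kept throughout, and a shared threshold does not erase it.

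**Conclusion.** The point holds in limited form. The plan rejects nulls at p < 0.05 in every tier below the primary, and the one procedure that might control the clinical tests has unclear scope and no content. Under no effect this means an 18% to 30% chance of at least one false rejection among the seven secondaries, and about 5 expected false rejections across the 102 to 104 subgroup tests.

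The secondary range rests on assumed correlations of 0.7 to 0. The subgroup count rests only on the listed measures and subgroups and on every test being run at 0.05. The interpretation of secondary and subgroup results is affected; the validity of the primary test is not.

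**What to change.** Revise Section 10.2 and the matching synopsis text before unblinding:

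- Limit the rejection rule to the primary endpoint at two-sided 0.05.
- Report subgroup and exploratory treatment effects as estimates with 95% CIs, without rejecting nulls.
- Report secondary results as supportive, with CIs and nominal p-values labelled as unadjusted. The exception is if the authors define the hierarchical procedure: endpoints covered, order, level, stopping rule, and sidedness for M/EEG.
- State in either case which tests the hierarchical sentence covers. The authors should settle this, because the documents do not.

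If formal secondary claims are wanted, Holm or a fixed sequence after the primary are options. Gating on the primary matters. Holm at 0.05 run alongside an ungated primary leaves the error across all eight at about 1 − 0.95 × 0.95 = 9.75% if the two parts are independent.

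Holm also has a real price. Its first step is 0.05 / 7 = 0.0071, where power for a lone secondary effect of f = 0.356 is about 0.53, against 0.80 at 0.05 (same reading as in the sample-size check). In 36 subjects that is a choice for the authors, not a requirement.

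The cost of the main change is wording. Fewer secondary or subgroup findings could be called significant; primary power and data collection are unchanged. ADAS-cog, ADCS-ADL and NPI also serve as safety measures (Section 7), and their safety readings should not be held to a stricter threshold.
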